7.11.2 Data Collection and Follow-Up for Withdrawn Subjects

Subjects who withdraw or are withdrawn from the study will not be replaced. Data collected prior to the withdrawal will be maintained and included in the data analysis.

7.12 Subject Compensation

Subject compensation for study participation will be detailed in the Informed Consent.

8 Data Collection and Analysis

A separate Statistical Analysis Plan (SAP) will be prepared for this study which will contain a detailed description of the statistical analysis. The SAP will be approved by the sponsor and the SAP sign-off will take place before the database lock. The sections below provide an overview and summary of the analyses to be detailed in the Statistical Analysis Plan.

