6.4.1 Sample Size

The efficacy of the patch will be assessed compared with no-patch use. The primary endpoint is the occurrence of being a NRS-responder at Day 5 defined as \geq 30% decrease from baseline of the instantaneous pain and no rescue medication. The responder proportion in the "no-patch" arm is unknown, and a variety of proportions of responders are envisaged. The targeted treatment effect size is medium (Cohen's H ranging from 0.42 to 0.45). Ninety evaluable subjects per group (180 evaluable subjects in total) are needed to reach 80% power, as shown in the following table.

Alpha N per Group **Responder Rate** Cohen's H (2 sided) No Patch Patch 90 5% 10% 27% 0.449 90 5% 20% 39% 0.422 90 5% 30% 51% 0.432 90 5% 40% 61% 0.423 90 5% 50% 71% 0.433 90 0.422 5% 60% 80% Powers are calculated using East 6.4

Table 2. Power Calculations

Further assuming a dropout rate of 10%, the expected number of subjects to be randomized is a total of 200. Subjects will be randomized 1:1 to the treatment and no patch arms. The estimated number to be screened to achieve 200 randomized subjects is 260.

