7.4 Blinding / Unblinding

This is an open label study, therefore there are no blinding / unblinding procedures.

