10.3 Case Report Forms and e-diaries

The study case report form (CRF) and the e-diary are the primary data collection instruments for the study. All data requested on the CRF must be recorded. All missing data must be explained.

A Case Report Form will be completed for each subject enrolled into the clinical study. The investigator-sponsor will review, approve and sign/date each completed CRF; the investigator's signature serving as attestation of the investigator's responsibility for ensuring that all clinical and laboratory data entered on the CRF are complete, accurate and authentic. The electronic system used for data recording will provide for electronic signatures and audit traceability.

E-diaries for subject self-reported data will be maintained independent of the CRFs. E-diary information will be captured in a separate database and will be reviewed for completeness.

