I, the undersigned declare that I have reviewed the statistical analysis plan along with TLF mockups and that to the best of my knowledge the document is internally consistent with protocol and scientifically rational. Reviewed by:

Signature:

Title: Project Manager

Organization: ICON plc

AUTHORIZATION: I, the undersigned, declare that I have reviewed the statistical analysis plan along with TLF mock-ups and that to the best of my knowledge the document accurately reflects the protocol objectives.

Authorized by:

Signature:

Title: Global Medical Statistician

Organization: Sanofi

CONFIDENTIAL Page 4 of 30

REVISION HISTORY

Version	Date	Author	Reasons
1.0	DEC 08, 2021		Initial Version.
2.0	SEP 12, 2022		Modification of the NRS response definition in the "Section 5.1.7.1 Primary analysis".
			Modification of the "Section 5.1.7.4.2 Use of rescue medication" to detail its definition and new protocol version with revised enrolment criteria.
3.0	DEC 01, 2022		Analysis Timepoints update according to the Memo to File (NTF 019 dated 22NOV2022).
			Addition of sensitivity analysis and corresponding Sensitivity Analysis Population.
			Addition of Full Analysis Set.
			Addition of MedDRA and WHO drug dictionary versions.
4.0	DEC 12, 2022		Modification of mITT, FAS, and Sensitivity Analysis Populations.
			Modification of the Time to Reach Acceptable Pain definition.
			Modification of Time-to-event endpoints analysis.
			Implementation of the analysis by actual treatment group for the Safety Population.

CONFIDENTIAL Page 5 of 30

LIST OF ABBREVIATIONS

Abbreviation or special term	Explanation
AE	Adverse Event
ANCOVA	Analysis of Covariance
CI	Confidence Intervals
CRF	Case Report Form
CTMS	Clinical Trials Management System
EOS	End of Study
EOT	End of Treatment
ET	Early Termination
FAS	Full Analysis Set
IA	Interim Analysis
ICF	Informed Consent Form
IQR	Inter Quartile Range
ITP	Infrared Therapy Patches
ITT	Intent-to-Treat
LS Means	Least-Square Means
MedDRA	Medical Dictionary for Regulatory Activities
mITT	Modified Intent-to-Treat
NRS	Numerical Rating Scale
NTF	Note to File
PAR	Pain Relief Score
PD	Protocol Deviation
PID	Pain Intensity Difference
PT	Preferred Term
Q1	First Quartile
Q3	Third Quartile
RMDQ	Roland-Morris Disability Questionnaire
SAE	Serious Adverse Event
SAP	Statistical Analysis Plan
SD	Standard Deviation
SDTM	Study Data Tabulation Model
ONFIDENTIAL	Page 6 of 30

Abbreviation or special term	Explanation

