5.1.7 Efficacy Analysis

5.1.7.1 Primary Analysis

Instantaneous pain on NRS will be summarized for actual values and change from baseline with descriptive statistics for the ITT and FAS populations by treatment group and by analysis timepoint (from Baseline to Day 5 Visit 2).

NRS-response will be defined as $\geq 30\%$ decrease from the baseline of the instantaneous pain and no rescue medication (Section 5.1.7.4.2).

CONFIDENTIAL Page 19 of 30

The number and percentage of NRS-responders at Day 5 Visit 2 will be presented descriptively by treatment groups, along with associated 95% confidence intervals.

The difference in the rate of responders at Day 5 Visit 2 will be tested between treatment groups using two-sided Fisher's exact test at the 5% error level (alpha = 0.05) and presented with its associated p-value. The null hypothesis H_0 that there is no difference in the rate of responders will be tested against the alternative hypothesis H_A that there is a difference in the rate of responders:

$$H_0: p_T - p_C = 0$$

$$H_A: p_T - p_C \neq 0$$

Where p_T denote the rate of responders at Day 5 Visit 2 in the FIRTECH Patch treatment group (treatment, T) and p_C denote the rate of responders at Day 5 Visit 2 in the No Patch treatment group (control, C). This analysis will be based on the mITT population.

A sensitivity analysis will be conducted by executing the primary endpoint analysis for subjects from the Sensitivity Analysis population. A list of subjects excluded from the Sensitivity Analysis population will be provided along with the reason for their exclusion.

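### The SAP deadline is database lock, but in this open-label trial lock does not separate analysis choices from results by arm. The risk is unprotected, not shown to have occurred, and cheap to close.

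*Protocol*

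**What the plan says.** Protocol section 8 sets the only deadline: "The SAP will be approved by the sponsor and the SAP sign-off will take place before the database lock". On masking, Protocol 7.4 says "This is an open label study, therefore there are no blinding / unblinding procedures", and SAP 2.6 repeats this. Neither document limits access to treatment codes or arm-level summaries for the statistician, the sponsor or the CRO, and neither links SAP approval to enrolment or to first access to data.

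The protocol fixes the core of the primary analysis (6.3.1, 8.3, 8.3.1.1): at least a 30% fall in instantaneous pain at the Day 5 on-site evaluation with no rescue medication, tested by Fisher's exact test at two-sided 5%. It does not name the population for that test in 8.3.1.1. The synopsis puts efficacy under the ITT paradigm, while 8.2 also lists an Evaluable for Efficacy set (NRS at baseline and Day 5). The endpoint definition gives no time window or list of therapies for rescue; SAP 5.1.7.4.2 supplies both.

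The SAP revision history records a changed NRS response definition and a more detailed rescue definition in version 2.0, and in version 4.0 "Modification of mITT, FAS, and Sensitivity Analysis Populations". Under SAP 4.1.2 the mITT set carries the primary test.

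**The concern.** In a blinded trial, signing the plan before lock works because arm and outcome cannot be connected until then. In this trial the arm is known throughout, so the same deadline would allow a plan to be revised after outcomes by arm could be tabulated. The protocol justifies unmasked participants because no true sham patch can be made. That reasoning does not extend to the people who write the analysis plan.

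What is at stake is the single primary test. If the analysed set or the detail of the responder rule could be chosen with the arms in view, the nominal 5% would no longer describe the procedure. Even if no such choice was made, the sponsor could not show from these documents that the definitions were independent of the results.

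**Working it through.** **1. Order of events (dates from the SAP revision history, SAP 1 and SAP 3.4).**

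| Date | Event |
|---|---|
| 8 Dec 2021 | SAP 1.0 |
| 22 Jul 2022 | Protocol version 4 |
| 12 Sep 2022 | SAP 2.0: NRS response definition modified, rescue definition detailed |
| 22 Nov 2022 | Note to file 019 on how e-diary entries were recorded |
| 1 Dec 2022 | SAP 3.0: FAS and sensitivity population added |
| 12 Dec 2022 | SAP 4.0: mITT, FAS and sensitivity population modified |

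SAP 5.1.2 summarises participants by protocol version (<4.0 / 4.0). This indicates that some were enrolled under a version before 22 July 2022, hence before SAP 2.0. The footnote to SAP Table 3 discusses recorded entries and subject-level deviations, so outcome data existed when versions 3.0 and 4.0 were written.

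**2. The plan's own figures.** The protocol states that "Ninety evaluable subjects per group (180 evaluable subjects in total) are needed to reach 80% power". The pooled-variance formula is n = [1.96·√(2p̄q̄) + 0.842·√(p₁q₁+p₂q₂)]² / (p₁−p₂)². For 20% against 39%, p̄ = 0.295, giving (1.264 + 0.531)² / 0.0361 = 89.3, so 90. Across Table 2 the requirement is 81 to 90 per arm, and 180/(1−0.10) = 200 randomised. The design figure reproduces.

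**3. Error with everything fixed in advance.** Enumerating all tables, Fisher's test at 90 per arm has a true size of 3.1–3.7% for common responder rates of 10–60%. With slightly unequal arms (for example 85 and 90) it is 4.2–4.9% for rates of 30–50%. A fixed plan therefore keeps the 5%.

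**4. Error if the definition could be chosen freely with results in view.** This was simulated with no true effect, 100 randomised per arm and 20,000 trials per scenario. The quantity counted is the share of trials in which at least one available definition gives Fisher p ≤ 0.05. The 10% missing at Day 5 is from the protocol. All other rates are assumptions:
- Rows marked a: pain response 50–70%, any rescue 20–40% (40% of it caught by a hypothetical Day-5-only rule), baseline NRS 0 in 3%, note-to-file exclusions 10–25%.
- Row marked b: pain response 50–60%, any rescue 20–30%, baseline NRS 0 in 3–8% and counted as non-response in the Evaluable set.

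| What is left open | Two-sided error |
|---|---|
| Nothing: mITT, any rescue is non-response (a) | 4.1–4.4% |
| mITT or Evaluable for Efficacy (b) | 4.5–5.0% |
| mITT or all randomised (a) | 4.6–5.5% |
| Two populations × two rescue rules (a) | 7.1–8.9% |
| Three populations × two rescue rules (a) | 8.5–11.5% |

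A further run, with other assumed rates, gave 5.9–8.9% once a second rescue rule and more populations were free. Taken together, the upper scenarios run from roughly 6% to 12%. The choice of population alone barely moves the error, because Fisher's conservatism absorbs it. Clear inflation needs a second rescue rule as well.

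**The case against.** The case against is strong on several points, and most of it stands.

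- The core of the responder rule is fixed in the protocol, and SAP 5.1.7.1 keeps it. The text of SAP 1.0 is not available, so the change in version 2.0 may only have aligned the SAP with the protocol. No second rescue rule appears anywhere.
- The mITT set has a protocol precedent. It is the Evaluable set minus participants with baseline NRS 0, whose percent change would divide by zero. That exclusion uses a pre-treatment value.
- No interim analysis is planned (SAP 5.1.10). Access controls may sit in the separate randomization plan named in Protocol 7.3, which is not among the documents.

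Three tempting inferences fail. Protocol 10.3 says "E-diary information will be captured in a separate database and will be reviewed for completeness"; that is a completeness check and does not show outcomes being reviewed by arm. The version 4.0 change to time to acceptable pain concerns a key secondary endpoint (SAP 5.1.7.2.4) and cannot affect the primary test. The clause in SAP 4.1.4 that lets exclusions be expanded after reviewing results covers only the sensitivity population.

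What remains is the gap itself. Lock is the only stated deadline, no role is masked, and primary definitions were revised while data were accruing, with no statement of who could see what.

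**Conclusion.** The point holds as a gap in control and documentation. The stated deadline does not protect the choice of primary definitions in an open-label trial, and the history of late revisions makes the gap practical. A reader might infer that arm-level results guided the changes, or that the 5% level has been lost. The documents support neither: they do not show that anyone viewed results by arm, and without that there is no inflation from this source.

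As to size, a free choice between mITT and Evaluable for Efficacy leaves two-sided error at about 5%. The range of roughly 6–12% is a worst case. It rests on assumed response, rescue and exclusion rates, and on a second rescue rule that is not documented. This is a cheap improvement, not a flaw that invalidates the primary analysis.

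**What to change.** 1. In Protocol section 8, require sign-off of the SAP, and of any later version, before data carrying the randomised arm are available to those who write or approve it. Until then, e-diary, deviation and population reviews use data with arm removed or dummy-coded. This cannot repair versions already written, but items 2 and 3 can still be done.
2. In SAP 2.6, state who had access to arm-level data when versions 2.0, 3.0 and 4.0 were written. If nobody who wrote or approved them did, that statement largely settles the matter.
3. Beside the mITT result, report the primary Fisher test on the protocol's own populations: all randomised, with missing Day 5 and baseline NRS 0 counted as non-response, and Evaluable for Efficacy, with baseline NRS 0 handled the same way. These sets can be built from the current documents. A rerun under SAP 1.0 would rely on definitions the reader cannot see.

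The cost is wording, dummy codes in data reviews and two further runs of an existing table. The downside is slightly more data handling and extra results that may be less favourable.

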8.1 Subject Descriptions

The Clinical Study Report will provide data listings at a per subject level. Demographics and baseline characteristics data will be summarized and reported using descriptive statistics (means, standard deviations, and ranges for quantitative variables and frequencies and percentages for qualitative variables) for each patch group for all subjects. Prior and concomitant therapies and medications will be included in the subject data listings, and will be summarized as per randomized assignment.

Protocol deviations will be listed by subject and summarized for each patch group by deviation type. Protocol deviations will also be reviewed for trends. Endpoint data will be summarized and analyzed as described below (Section 8.3).

8.2 Subject Population(s) for Analysis

The subject populations for analysis include the following:

- The Intent-To-Treat (ITT): any subject randomized into the study, regardless of compliance with study procedures.
- Evaluable for Efficacy: any subject randomized into the study that had the NRS evaluation done at baseline and day 5.
- Safety: any subject randomized into the study and, if randomized to the "patch" arm, had the device installed.

8.3 Statistical Methods

Descriptive analyses will include summary statistics (using n, mean, standard deviation, inter quartile range, median, minimum, and maximum) for quantitative variables or number and percentage of subjects in each category for qualitative data. When requested, all statistical tests will be conducted at 2-sided using 5% alpha level. Besides, multiplicity for secondary parameters will be considered in the SAP.

8.3.1 Efficacy Analyses

8.3.1.1 Primary Analysis

Descriptive analysis will be conducted for the instantaneous pain on NRS (A Numerical Rating Scale^[3]). The summary statistics will be presented for observed values at Day 5 and change from baseline to Day 5 for each group (patch, no-patch).

The rate of NRS-responders at Day 5 where NRS-response is defined as \geq 30% decrease from baseline of the instantaneous pain and no rescue medication will be presented descriptively for each group (patch, no-patch), along with an associated 95% confidence interval.

The hypothesis that there is no difference in the rate of responders will be tested between the group with patch and no-patch group at Day 5 using Fisher's exact test and presented with its associated p-value.

8.3.1.2 Secondary Analyses

Under the secondary analyses (key and other), descriptive and inferential analysis, where applicable, will be conducted for the following:

- Normalized Sum of Pain Intensity Difference (SPID₀₋₅): the descriptive and inferential analyses will be conducted for Day 5.
- Roland-Morris Disability Questionnaire^[5] (RMDQ) score: descriptive analysis will be conducted for the observed values at baseline and Day 5, as well as for change (improvement (%)) from baseline to Day 5. Inferential analysis will be conducted for change (improvement (%)) from baseline to Day 5.
- Mobility evaluation^[6,7]: descriptive analysis will be conducted for the observed values at baseline and Day 5, as well as for change from baseline to Day 5. Inferential analysis will be conducted for change from baseline to Day 5.
- Time to reach acceptable pain and time to reach no pain: descriptive and inferential analysis will be conducted based on the data obtained in between baseline and final visit assessments.
- Normalized Sum of Pain relief (TOTPAR₀₋₅): the descriptive and inferential analyses will be conducted for Day 5.
- Time course of PID and time course of Pain relief (VRS): descriptive analysis will be conducted for the observed values from baseline to Day 5.
- Frequency of Adverse Events: descriptive analysis will be conducted based on the data obtained in between baseline and final visit.

The inferential analysis for the Normalized Sum of Pain Intensity Difference (SPID₀₋₅), Roland-Morris Disability Questionnaire^[5] (RMDQ) score, Mobility evaluation^[6,7], Normalized Sum of Pain relief (TOTPAR₀₋₅), will be based on the analysis of covariance (ANCOVA) model with the group (patch, no-patch) as fixed effect and baseline pain intensity as a continuous covariate. The Least-Square Means, Standard Errors and 95% Confidence Intervals for each group (patch, no-patch) will be estimated and provided, along with the Least-Square Means, Standard Errors and 95% Confidence Intervals for the difference between group with patch and no-patch group. Additional effects will be added to the model in case of need.

The inferential analysis of time-to-event endpoints (time to reach acceptable pain, time to reach no pain) will include summary, display, and analysis using Kaplan-Meier estimation method. The comparison of survival distributions between the group with patch and no-patch group will be done by the Log-Rank test. During the analysis, if the event if interest never occurs, the time will be censored at the final visit.

These analyses will be based on the ITT population, using the ITT paradigm (i.e. as randomized).

8.3.1.3 Exploratory Analyses

The exploratory analyses will consist from:

- Assessing the frequency of use of Rescue Medication: descriptive analysis will be conducted for the observed values at baseline, baseline to Day 5 period and Day 5 assessments (through eDiary entries).
- Descriptions of "worst pain", "least pain" and "average pain": descriptive
 analysis will be conducted for the observed values at baseline, baseline to
 Day 5 period and Day 5 assessments, as well as for change from baseline
 to Day 5.

Inferential analysis for description of "worst", "least" and "average" pain will be conducted similar to secondary endpoints analysis for change from baseline at Day 5 using analysis of covariance (ANCOVA) model.

8.3.1.4 Compliance Analysis

8.3.1.4.1 eDiary Compliance (%)

Compliance will be measured based on the completion of e-Diaries. Subject will be considered as compliant if at least 80% of e-Diaries are completed, otherwise, if less than 80% of e-Diaries are completed, subject will be considered as non-compliant.

Descriptive statistics (e.g. mean, median, etc.) will be provided for the compliance (%), as well as summarized in categories: "<80%", "80% - 100%" using frequency tables. The number and percentage of compliant and non-compliant subjects will be presented as well, using the ITT paradigm (i.e. as randomized) and safety populations.

8.3.1.4.2 Patch use Compliance (Days)

Patch Use Compliance will be measured based on the number of days subject wears a patch. Subject will be considered as compliant if a patch is worn at

least for 4 days. Otherwise, if less subject wears a patch for less than 4 days, subject will be considered as non-compliant.

Descriptive analysis will be conducted for Patch Use Compliance (Days), as well as Patch Use Compliance (Days) will be summarized in categories: "1 day", "2 days", "3 days", "4 days", "5 days" and ">5 days" using frequency tables. The number and percentage of compliant and non-compliant subjects will be presented as well, using the ITT paradigm (i.e. as randomized).

8.3.1.5 Adjustments for Multiple Testing

Adjustment for multiple testing will be done as follows:

- The multiplicity of key secondary endpoints will be handled using a False Discovery Rate (FDR) approach. Nominal p-values will also be displayed.
- For the other secondary endpoints and the exploratory endpoints, p-values will be provided for descriptive purpose only.
- The number of adverse events defined as other secondary endpoint will be analyzed only with descriptive statistics (no p-value will be provided).

8.3.2 Safety Analyses

8.3.2.1 Adverse Events

Adverse events are defined as listed in Section 9.1. Adverse event reporting for the purposes of regulatory compliance is described in Section 9.4.

The Adverse Events will be summarized by frequencies and percentages of subjects with at least one AE and presented in the Clinical Study Report using the Safety population and the "as treated" paradigm (i.e. according to if they actually had a patch installed, or not).

8.3.2.2 Other Safety Analyses

Safety assessments (Vital Signs, Physical Examination, etc.), concomitant medications and procedures, will be reported using descriptive statistics, if applicable, and frequencies and percentages. The safety summaries will be based on the Safety population and under the "as treated" paradigm (i.e. according to if they actually had a patch installed, or not).

9 Safety and Adverse Events

